If a PrEP candidate has an identifiable HIV-positive partner, we will attempt to obtain genotypic information about the partner's virus, in order to avoid offering Truvada® PrEP in a situation of likely exposure to a virus already resistant to both component drugs of Truvada®. We will ask the PrEP candidate to try to obtain a de-identified genotype of the seropositive partner. We will assist in providing a release of confidential medical information form for this purpose. In the event that the seropositive partner is a patient at DYC, we will ask the seropositive partner to sign a 'Release of Information' allowing the PrEP participant and the CRUSH team access to his genotype. If a CRUSH medical provider has confirmed documentation that the seropositive partner's virus is resistant to both drugs in Truvada®, or has reason to believe that this is likely the case, then the PrEP patient will be excluded from receiving Truvada® PrEP as part of CRUSH, and will be referred for expert medical consultation regarding other options. If we are unable to obtain a genotype or resistant records for the seropositive partner, and have no reason to believe that two-drug resistance is likely, we will offer Truvada® PrEP as usual.

VII.7 PrEP Initiation

The PrEP initiation visit will take place 1-2 weeks after screening, when all screening results are available. If the participant is eligible to receive PrEP, the clinician will review all lab results done at the screening visit, repeat a rapid oral HIV antibody test, and obtain a medical history along with a focused review of systems. All participants who are determined to be HBsAg negative and who do not have antibodies to hepatitis B will be offered the hepatitis B vaccination series. If high risk exposure, as described in section VI 1.1, or signs and/or symptoms suggestive of acute retroviral syndrome have occurred since the screening visit, PrEP will be withheld and the participant will be managed in accordance with the guidelines specified in the screening visit. Further STI testing will also be done if indicated. Women of reproductive potential will have a rapid urine pregnancy test. If no contraindications to receiving PrEP have been established, the risks and benefits of FTC/TDF (Truvada®) for PrEP will be reviewed, and all questions and concerns will be addressed. The participant will be instructed to take FTC/TDF daily, at the same time every day. The study coordinator or other DYC staff

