member will provide risk reduction counseling, provide the participant with condoms, and schedule a follow up visit for 4 weeks. When all study activities for the day are complete and documented on a dispensing checklist, the pharmacy will dispense one bottle (30 pills) of Truvada® to the participant.

Participants found to be hepatitis B antigen positive, who choose not to take PrEP, will be referred to either their primary care provider or another community based clinic for treatment of hepatitis B infection. Participants who are HBsAg-positive and who initiate PrEP will be informed that stopping PrEP could cause a hepatitis flare and/or hepatitis B drug resistance. The clinical stage of their liver disease will be assessed at PrEP initiation (see Appendix Q), including testing for AST/ALT, total bilirubin, alkaline phosphatase, prothrombin time, and albumin, and a clinical evaluation for stigmata of cirrhosis. Participants who are HBsAg positive and who receive PrEP will have their hepatitis B DNA viral load and their AST/ALT monitored for the duration of their PrEP use and for 6 months following discontinuation of PrEP.

VII.8 One Month Visit

At the 1-month visit, participants will have a rapid HIV antibody test, sexual health promotion counseling, and PrEP-specific counseling. Participants will meet with the study clinician for a medical history and targeted physical exam. For participants who are still interested in receiving PrEP, a blood sample will be drawn for creatinine and for dried blood spot (DBS) testing of drug levels. Additionally for those participants who are HBsAg positive, blood will be drawn for ALT/AST and hepatitis B DNA. Participants who remain eligible to receive PrEP will be provided two bottles (60 pills) at this visit. Women of reproductive potential will have a rapid urine pregnancy test.

VII.9 Subsequent visits

Subsequent visits will occur according to the schedule shown in the table of Study Procedures. Following the 1 month follow up visit, participants will be asked to return to the clinic in 2 more months (at 3 months of participation), and then every 3 months thereafter for study visits (i.e., at months 3, 6, 9

and 12). These visits will be scheduled within +/- 2 weeks of the target date based on PrEP initiation. Participants who elect to continue PrEP beyond 48 weeks will continue to be assessed every 3 months for the duration of the project period, or until they cease PrEP.

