At quarterly visits, participants will receive rapid HIV testing and counseling, and will meet with a clinician for a medical history. If they report a possible STI exposure or have symptoms of an STI, they will be tested and treated as appropriate. Participants will also receive PrEP-specific counseling, be asked to provide a blood sample for creatinine and for dried blood spot (DBS) drug level testing, and be dispensed 3 bottles (90 pills) of PrEP. Women of reproductive potential will have a rapid urine pregnancy test at all scheduled visits. At semiannual visits, in addition to the quarterly procedures, participants will have STI and serum HIV antibody testing done, a targeted physical exam will be performed, and they will be asked to complete an ACASI questionnaire. Participants who are HBsAg positive will have ALT/AST and HBV DNA viral load testing done.

VIII. Assessments and Interventions

Assessments and interventions taking place at each visit are described below.

VIII.1 Risk assessment and clinician counseling

Risk assessments will be conducted using "Five P's," a simple approach to risk assessments for clinicians recommended by the California STD Prevention Branch (CA STD Branch, 2011).⁸ The five P's stand for Partners, sexual Practices, Past STIs, Pregnancy history and plans (if relevant), and Protection from STIs. Sexual risk information will be entered into the clinical notes. The clinician will document performance of a risk assessment on the Dispensing Checklist, and perform brief counseling regarding risk reduction.

VIII.2 Pregnancy and breastfeeding assessment and counseling

Female participants of reproductive potential (anatomically female, premenopausal, with an intact uterus) will be screened at each visit for pregnancy, plans to become pregnant, and current breastfeeding.

All women who are pregnant at enrollment or become pregnant during their participation will be immediately linked to prenatal care. The clinician will:

- a. Determine if women are planning to become pregnant, are currently pregnant, or are breastfeeding;
- b. Disclose to women that safety for infants exposed to Truvada® during pregnancy has not been fully assessed but that no harm has been reported;
- c. Do not offer (or, if already begun, cease) PrEP to women who are breastfeeding;
- d. Conduct a pregnancy test and document results; if pregnant, discuss continued use of PrEP with patient and prenatal care provider;

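### The stated PrEP dispensing does not reach the late edge of the ±2-week visit window at weeks 12 and 24

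*Protocol*

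**What the plan says.** Dosing (Protocol VII.7): "The participant will be instructed to take FTC/TDF daily, at the same time every day".

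Supply: at initiation "the pharmacy will dispense one bottle (30 pills) of Truvada® to the participant", and staff "schedule a follow up visit for 4 weeks" (VII.7). At the one-month visit, participants still eligible "will be provided two bottles (60 pills) at this visit" (VII.8). At each quarterly visit they will "be dispensed 3 bottles (90 pills) of PrEP" (VII.9).

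Timing (VII.9): "Subsequent visits will occur according to the schedule shown in the table of Study Procedures". The only visit table in the text available is Appendix 4, whose quarterly columns are weeks 12, 24, 36 and 48. VII.9 also lists months 3, 6, 9 and 12. On tolerance it says: "These visits will be scheduled within +/- 2 weeks of the target date based on PrEP initiation".

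Dispensing after initiation (VIII.10) is described as taking place at scheduled visits once eligibility is confirmed. VIII.11 adds a reminder a week ahead of each visit, at which the date may be changed, and a check-in half-way between quarterly visits. Neither mentions how many pills the participant has left.

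**The concern.** The dispensing rule and the window rule are both anchored to PrEP initiation, so they can be compared day by day. The bottles match the planned intervals. The window, however, allows a visit later than the supply lasts at the first two quarterly visits.

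What is at stake is continuity of PrEP for a participant who does exactly what the protocol asks: takes every dose and attends on a permitted date. The pill count, visit dates and question about recent doses (VIII.3) would let staff recognise a run-out afterwards, but would not prevent it.

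**Working it through.** **Inputs.** One pill a day (VII.7). Pills: 30 at day 0, 60 at week 4 (day 28), 90 at each quarterly visit (VII.7 to VII.9). Quarterly targets: 12, 24, 36 and 48 weeks × 7 = days 84, 168, 252 and 336 (Appendix 4). Window: ±14 days (VII.9).

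**Conventions assumed.** No dose is skipped while pills are in hand. The first dose is taken on day 0. The dose on a visit day comes from the new supply. The week-4 pills are collected by day 30; on day 28 there are 30 − 28 = 2 left.

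**The plan's own figures.** 3 bottles × 30 = 90 pills, as stated. Total dispensed before each quarterly visit: 30 + 60 = 90, then 180, 270 and 360.

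**Supply against target and late edge.** Spare pills = total dispensed − day of visit; a negative value is a shortfall.

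| Visit | Pills before visit | Target day | Spare on target | Latest day | Spare at latest day |
|---|---|---|---|---|---|
| Week 12 | 90 | 84 | 6 | 98 | −8 |
| Week 24 | 180 | 168 | 12 | 182 | −2 |
| Week 36 | 270 | 252 | 18 | 266 | 4 |
| Week 48 | 360 | 336 | 24 | 350 | 10 |

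**Days affected.** A week-12 visit on day 90 misses 0 doses, on day 91 it misses 1, and on day 98 it misses 8. So days 91 to 98 are affected, 8 of the 29 permitted days (70 to 98). With week 12 held by day 90, a week-24 visit on day 180 misses 0, on day 181 it misses 1, and on day 182 it misses 2: 2 of 29 permitted days (154 to 182).

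**Carry-over between the two visits.** Let week 12 fall on day v and week 24 on day w.

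- If v ≤ 90, doses missed before week 24 = max(0, w − 180), at most 2.
- If v > 90, nothing is left over and the new 90 pills start on day v, so doses missed = max(0, w − v − 90). With w = 182 this is 1 for v = 91 and 0 for v ≥ 92.

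So (91, 182) is the only pair with a gap at both visits, one dose each. The largest total over both visits is 8 (v = 98, then none before week 24).

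**First dose on day 1 instead.** 98 − 1 − 90 = 7 and 182 − 1 − 180 = 1.

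**Calendar-month reading.** With a month of 365.25/12 days, months 3, 6, 9 and 12 fall on about days 91, 183, 274 and 365, with late edges at 105, 197, 288 and 379. Subtracting 90, 180, 270 and 360 pills gives shortfalls of 15, 17, 18 and 19 days at the late edge, and of 1, 3, 4 and 5 days even on target. Each is the total shortfall to that date.

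**The case against.** The strongest reply is that nothing is miscalculated. The bottles fit the planned intervals with pills to spare, and the window is a scheduling tolerance, not a promise of supply. A gap needs near-complete adherence, a visit late in the window, and staff who do not step in. Every skipped dose leaves a spare pill. This stands as a limit on how often the problem would arise. The 8 of 29 and 2 of 29 are counts of permitted days, not frequencies; the documents give no distribution of visit dates. It does not remove the problem for the participant who follows the instructions exactly.

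A second reply is that the site has a pharmacy, as-needed visits, a mid-way check-in and a reminder call, so staff would simply refill. Nothing in the text forbids that. The dispensing checklist is not reproduced and some appendix pages are not in the text reviewed, so the statement here is limited to what is visible: dispensing after initiation is described only at scheduled visits, and neither contact is tied to pills in hand. The mid-way check-in is a real opportunity to catch a late week-24 visit. Read literally, it falls between quarterly visits and may not cover weeks 4 to 12.

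Two stronger readings are tempting and are not supported:

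- HBsAg-positive users are "informed that stopping PrEP could cause a hepatitis flare and/or hepatitis B drug resistance" (VII.7), and a reader might infer that a run-out exposes them to this. The documents do not equate a gap of at most 8 days, on the week schedule, with stopping.
- A reader might apply the window to the one-month visit, where 30 pills against day 28 + 14 = 42 would be 12 short. The window sentence follows the list of months 3 to 12, so its application to week 4 is not clear, and no gap is claimed there.

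**Conclusion.** The point holds as a minor operational gap. On the week schedule, a fully adherent participant can miss up to 8 doses before week 12 or up to 2 before week 24 (7 and 1 if dosing starts the day after dispensing), and at most 8 over both.

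The result rests on full daily adherence, a week-4 pick-up by day 30, no refill outside scheduled visits, and the week targets. The week reading is the better supported, since VII.9 defers to the visit table and itself refers to continuing beyond 48 weeks. It is also the reading kinder to the plan: on calendar months every quarterly visit can run short. The choice of targets therefore needs to be written down.

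No size of harm is claimed, and no endpoint or analysis has been shown to be affected.

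**What to change.** In VII.9, state that the quarterly targets are weeks 12, 24, 36 and 48 from PrEP initiation. Set the latest permitted date at day 90 for week 12 (84 + 6) and day 180 for week 24 (168 + 12), and keep +14 days thereafter. At both caps the shortfall is zero (90 − 90 and 180 − 180). The week wording is essential: on calendar months the first target, about day 91, would already lie past the day-90 cap.

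In VIII.11, have staff check the run-out date at the mid-way contact and at the reminder call. In VIII.10, allow one bottle to be dispensed early, after the HIV test required for dispensing, when a participant cannot attend by the cap. Thirty pills exceed the largest week-schedule gap of 8. Record the early bottle so that the next pill count is read correctly.

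The cost is a few sentences, a slightly tighter late window at two visits, and an occasional early bottle with its visit.

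A simpler alternative is one extra bottle at week 4. It gives 120 pills against day 98 and 210 against day 182, and on calendar months 120, 210, 300 and 390 against 105, 197, 288 and 379. It tightens no window, but every participant then holds 30 more pills.

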Appendix 4:

Study Visit Schedule

Study Visit Schedule (

Week	Screening*	0	4	12, 24, 36, 48		Stop drug	HIV Ab+
Clinical Assessments/Interventions							
Screen inclusion/exclusion criteria	x						
Obtain informed consent	x						
Medical history and focused review of systems	x	x	x	x		x	x
STI Risk Assessment	x	x	x	x		x	x
Adherence Assessment			x	x		x	x
Targeted Physical Exam	x	x	x	x		x	x
Adherence counseling		x	x	x		x	x
Risk reduction counseling, condom distribution	x	x	x	x		x	x
Drug dispensing		x	x	x			
ACASI (weeks 0, 4, 24, 48 only)		x	x	x			
Laboratory Assessments							
Creatinine	x		x	x			
Urine dipstick protein	x	x	x	x			
Rapid urine pregnancy test (if relevant)	x	x	x	x		x	x
HBsAg (and HBsAb if not documented)	x						
ALT/AST (if HBsAg+)		x	x	x		x	x
HBV DNA + LFTs(if HBsAg+)		x	x	x		x	x
Serum HIV Ab EIA	x					x	
Rapid Oral HIV Ab	x	x	x	x		x	
HIV Ab Western Blot							x
HIV RNA Qualitative PCR	x						
HIV RNA Qualitative PCR (risk-guided)			x	x		x	
HIV RNA Quantitative PCR							x
HIV-1 genotype							x
STI laboratory evaluation	x			x		x	x
DBS Drug Level Testing			x	x		x	x
*-4 to -1 weeks September 2013						Page 40 of 53	

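### Protocol VII.9 requires serum HIV antibody testing at weeks 24 and 48 on PrEP, but the Appendix 4 visit table leaves it out

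*Protocol*

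**What the plan says.** Section VII.9 gives participants on PrEP a rapid HIV test at each quarterly visit and then adds a second layer: "At semiannual visits, in addition to the quarterly procedures, participants will have STI and serum HIV antibody testing done". The serum test is therefore separate from the rapid test and additional to it. The same section sends staff to a table for the timetable: "Subsequent visits will occur according to the schedule shown in the table of Study Procedures".

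The only visit table in the supplied documents is Appendix 4, titled Study Visit Schedule. It pools weeks 12, 24, 36 and 48 in one column. Its HIV testing rows for participants not known to be infected read as follows.

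| Row | Screening | Wk 0 | Wk 4 | Wks 12–48 | Stop drug |
|---|---|---|---|---|---|
| "Serum HIV Ab EIA" | x | | | | x |
| "Rapid Oral HIV Ab" | x | x | x | x | x |
| HIV RNA qualitative PCR | x | | | | |
| "HIV RNA Qualitative PCR (risk-guided") | | | x | x | x |

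On nucleic acid testing (NAT), VII.3 sends a sample from every HIV-negative participant at every visit. Appendix 12 collects it only from HIV-negative participants who are not on PrEP.

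**The concern.** Text and table give different HIV testing schedules to people who are being given further supplies of Truvada. Because VII.9 itself refers staff to the table, it is not safe to assume that the text will prevail in the clinic. Section VIII.7 has staff confirm before dispensing that all required specimens were submitted, and at weeks 24 and 48 what counts as required depends on which page they use.

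If Appendix 4 is followed, and Appendix 12 is followed on NAT, the only unconditional HIV test between Screening and Stop drug is the oral rapid test. The RNA test in that period is ordered according to risk. Appendix 4 pairs the serum and rapid tests at Screening and Stop drug, so the plan does not treat one as a substitute for the other. At stake is a scheduled blood-based check for infection while a participant continues on two antiretroviral drugs, a setting in which Appendix 13 regards resistant virus as a matter for close watching.

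**Working it through.** **1. Which weeks are semiannual.** VII.9 lists months 3, 6, 9 and 12, and Appendix 4 lists weeks 12, 24, 36 and 48. Month 6 is therefore week 24 and month 12 is week 48. The questionnaire confirms this: VII.9 places it at semiannual visits, and the table row reads "ACASI (weeks 0, 4, 24, 48 only").

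**2. Whether the blank cell is an artefact.**
- Pooling four weeks in one column can put a tick where only some weeks apply. It cannot remove one.
- VII.9 adds four items at semiannual visits for all PrEP participants: STI testing, serum HIV antibody, a targeted physical exam and the questionnaire. Three of the four are ticked in the pooled column. Only the serum test is not.
- The questionnaire row shows how the table limits a tick to named weeks. The serum row has neither a tick nor such a label.
- The other rows align with the column heads. The unlabelled column before Stop drug is empty in every row, so it is not a lost semiannual column.

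**3. Scheduled serum tests lost if Appendix 4 is followed.** VII.9 gives 2 on-treatment tests through week 48 (weeks 24 and 48). Appendix 4 gives 0 until Stop drug.

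| PrEP stops | Tests lost |
|---|---|
| At or before week 24 | 0 (at week 24 the Stop drug test replaces the semiannual one) |
| After week 24, before week 48 | 1 (week 24) |
| At week 48 | 2 − 1 = 1 (the Stop drug test replaces the second) |
| Not by week 48 | 2 − 0 = 2 through week 48 |

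Appendix 4 has no column after week 48, so later tests are not counted.

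**4. Interval from the screening serum test to the next, for a participant on PrEP to week 48.** Interval = week of next serum test + weeks from screening to week 0. Two screening intervals appear: "The PrEP initiation visit will take place 1-2 weeks after screening" in VII.7, and −4 to −1 weeks in the Appendix 4 footnote. The visit window comes from VII.9: "These visits will be scheduled within +/- 2 weeks of the target date based on PrEP initiation".

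| Basis | VII.9 (next test week 24) | Appendix 4 (next test week 48 or later) |
|---|---|---|
| Nominal, 1–2 weeks | 24+1 to 24+2 = 25–26 | at least 48+1 to 48+2 = 49–50 |
| Nominal, 1–4 weeks | 24+1 to 24+4 = 25–28 | at least 48+1 to 48+4 = 49–52 |
| With visit window, 1–2 weeks | 22+1 to 26+2 = 23–28 | 46+1 to 50+2 = 47–52 |
| With visit window, 1–4 weeks | 22+1 to 26+4 = 23–30 | 46+1 to 50+4 = 47–54 |

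The last two Appendix 4 entries assume that PrEP stops at the week 48 visit.

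**5. Drug dispensed before the next serum draw.** VII.7, VII.8 and VII.9 dispense 30, 60 and 90 pills at initiation, month 1 and each quarterly visit.
- VII.9 (weeks 0, 4, 12): 30 + 60 + 90 = 180 pills in 3 dispensings.
- Appendix 4, stopping at week 48 (weeks 0, 4, 12, 24, 36): 30 + 60 + 90 + 90 + 90 = 360 pills in 5 dispensings.

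**The case against.** The strongest reply is that this is a one-row editorial slip under explicit body text, in a study with several other safeguards. A rapid test is done at every quarterly visit. RNA testing is available when risk suggests it, section IX.3 provides a work-up for suspected acute infection, and any positive test triggers a seroconversion visit. If VII.3 governs NAT, blood is tested for virus at every visit and the missing serum test matters much less. The pill counts do not measure harm, because a rapid test is scheduled at each of those dispensing visits. Appendix 13 concerns resistance assays in people already infected and says nothing about how often uninfected users should be tested.

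Much of this is fair, and it limits the finding. What is lost is a scheduled back-up, not HIV testing as such. Appendix 13 shows why late detection would matter but sets no testing frequency. The point is an internal inconsistency, not a criticism of a deliberate design decision.

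It does not remove the conflict. VII.9 hands the timetable to the table, so the text cannot simply be presumed to win. NAT cannot be relied on to fill the gap while Appendix 12 excludes PrEP users. The pre-dispensing check in VIII.7 helps only if the checklist names the serum test, and its contents are not in the supplied text. VII.9 calls its table by a slightly different name, but no other visit table was supplied.

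**Conclusion.** The concern holds. VII.9 and Appendix 4 conflict on serum HIV antibody testing during PrEP, and the table should be corrected. Following the table costs one scheduled serum test for participants who stop PrEP after week 24 and up to week 48, and two through week 48 for those who continue. For a participant on PrEP to week 48, it moves the next serum test from about half a year after screening to about a year or later.

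This rests on Appendix 4 being the table that VII.9 means, and on a Stop drug visit taking place. A participant who passes week 24 and is lost without that visit would, under the table, have no scheduled serum test after screening. The documents give neither assay sensitivity nor HIV incidence, so the number of infections detected late cannot be estimated, and no effect on a particular endpoint is claimed.

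**What to change.** In Appendix 4, mark the serum HIV antibody row in the pooled follow-up column and label it as applying at weeks 24 and 48 only, in the style of the questionnaire row. Add that it continues every 6 months while PrEP continues. For visits after week 48, VII.9 states only 3-monthly assessment, so that extension is a reading of VII.9 that the sponsor should confirm. If the sponsor in fact intended the table, VII.9 must be amended instead.

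Separately, make VII.3 and Appendix 12 agree on whether participants receiving PrEP have NAT. The documents do not show which version was meant, so the sponsor has to choose.

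The cost is one labelled table entry and one sentence on NAT. VII.9 already requires the serum tests at weeks 24 and 48, and blood is already taken at every quarterly visit for creatinine and drug levels. The serum correction therefore adds no visit and no blood draw.
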